6.3.6 End of Study and Follow-Up

At Month 7, participants will complete a long battery of surveys they have been completing throughout the study; additional surveys are the CSQ and Program Evaluation Surveys. If a participant is randomized to an intervention group but discontinues participation in the study for any reason prior to Month 7, they will be asked to complete the CSQ and Program Evaluation Surveys. Adverse Events are assessed by research coordinator contacts bi-weekly throughout the study. If a participant withdraws from the study early for any reason, we will complete this assessment at that time.

6.3.7 Removal of Subjects

Phase 1: Participants will be removed if they choose to voluntarily withdraw.

Phase 2 and 3: Participants will be removed if they choose to voluntarily withdraw. Participants will be removed if they no longer meet any study inclusion/exclusion criteria (for example, if they do not have diary-

confirmed migraine, or if they initiate a new migraine medication during the study). Participants who withdraw for any reason will be given the option of continuing to use the app if they choose.

All participants will be provided with a synopsis of their diary data to be used in their routine clinical care following the study.

6.4 Statistical Method

6.4.1 Statistical Design

Basic descriptive statistics (e.g., means, standard deviations, frequencies) for variables of interest will be computed. Graphical approaches will be used to further explore the data where appropriate. The outcomes are either 1) repeated measures of binary adherence to each migraine management strategy [coded each day as 0 (did not adhere) or 1 (adhered)] or total number of non-adherence days for each migraine management strategy over the relevant time-frame. Longitudinal binary outcomes will be analyzed using randomized logistic models, and number of total non-adherence days will be examined using Poisson regression models. SAS 9.3 will be used in the analyses. All tests are two-sided using significance level 0.05.

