3.3.1 POTENTIAL BENEFITS

Individual study participants, may experience improved knowledge about their own adherence to migraine management strategies, as well as daily variations in headache symptoms, stress and sleep. Participants may experience improvements in their adherence to migraine management strategies, and potentially experience improvements in their migraine management. Regarding societal benefits, this study will identify patterns of individual differences and circumstances associated with migraine management adherence. This will allow for tailored interventions to improve migraine management adherence in the patients who experience the most difficulty with adherence. This study will also test the feasibility and obtain initial effect sizes for a novel tailored intervention to improve patient adherence to migraine management strategies. If successful, this intervention could improve adherence to migraine management strategies, and potentially improve the effectiveness of migraine treatments.

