4. STUDY OBJECTIVES

4.1 HYPOTHESIS

Primary: We hypothesize that higher education, income and outcome expectancies, female gender, and lower rates of psychiatric comorbidities, will be associated with improved adherence to preventive and acute migraine management strategies.

Secondary: We hypothesize that the use of the CDST will increase adherence to preventive and acute migraine management strategies compared to Headache Education.

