5.2 OUTCOME VARIABLES

5.2.1 PRIMARY OUTCOME VARIABLES

The primary outcome variables will be **adherence to acute and preventive migraine management strategies**. All primary outcome variables will be assessed through an electronic headache diary.

Adherence to Acute Migraine Management Strategies.

- a) **Treat Early:** When participants record headache activity, they will record type, timing, and current pain level for each acute medication dose taken. Treating early is operationalized as taking acute medication while the pain is mild.
- b) **Avoid Overuse:** Avoiding overuse is operationalized as taking fewer than 10 triptans and 15 non-specific pain medications (NSAIDs and acetaminophen) per month.

Adherence to Preventive Migraine Management Strategies:

- a) **Adherence to Preventive Behavioral Strategies:** Each participant will record information related to a single strategy: stress management, sleep management, or consistent eating. Participants will record either 1) whether they used a stress management strategy today (assessed each evening; Yes = adherent, No = non-adherent), or 2) when they got in and rose out of bed (consistent bedtime and rise-time; assessed each morning; Within 1 hour of median = Adherent, outside of 1 hr of median = Non-adherent).

Adherent), or 3) whether they ate at least three times that day (consistent eating, assessed each evening; Yes = Adherent, No = Non-adherent).

b) **Adherence to Preventive Medication:** If a participant is taking a preventive medication, they will record whether they took preventive medication each day. Taking preventive medication = Adherent, Not taking preventive medication = Not-adherent.

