6.4.3.2 Secondary Objectives Analyses

Secondary Objective: Develop a tailored CDST to improve preventive and acute migraine management strategies.

Phase 3 diary data will be utilized. As described above, random effects logistic models will be used to examine the effects of Group (CDST vs. Headache Education Control), Time, and Group X Time on daily adherence to migraine management strategies. Poisson regression model with log of length of follow-up as offset will be used to examine differences between the groups on total number of nonadherence days at the end of the study.

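### Four unranked primary adherence outcomes, each given two models at 0.05 with no deciding test: under no effect, Phase 3 has about a 19–34% chance of at least one nominally significant group difference

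*Combined protocol and SAP*

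**What the plan says.** Section 5.2.1 speaks of primary outcomes in the plural: "All primary outcome variables will be assessed through an electronic headache diary". It defines four, repeated in 6.2.1 (Efficacy), and ranks none:

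- Treat early: "Treating early is operationalized as taking acute medication while the pain is mild". Pain level is logged dose by dose.
- Avoid overuse: "Avoiding overuse is operationalized as taking fewer than 10 triptans and 15 non-specific pain medications (NSAIDs and acetaminophen) per month". This is a monthly threshold, not a daily yes or no.
- Preventive behavior: "Each participant will record information related to a single strategy: stress management, sleep management, or consistent eating".
- Preventive medication, recorded daily but only by participants who take one.

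Section 6.4.1 lists two forms of outcome, daily binary adherence and total non-adherence days, and says: "All tests are two-sided using significance level 0.05". For Phase 3, section 6.4.3.2 fits a random effects logistic model with Group, Time and Group X Time, and then: "Poisson regression model with log of length of follow-up as offset will be used to examine differences between the groups". Section 6.4.3.1 pairs the same two models for the Phase 2 predictors. Section 4.1 hypothesises effects there for "higher education, income and outcome expectancies, female gender, and lower rates of psychiatric comorbidities"; 6.4.3.1 gives its predictors only as examples, one of which, age, is not in that list. Section 6.4.4 adds unadjusted and adjusted versions if the randomized groups differ at baseline.

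Section 3.3.1 (Potential Benefits) gives the pilot's aim: "This study will also test the feasibility and obtain initial effect sizes for a novel tailored intervention".

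**The concern.** With several primary outcomes, two models for each and the full 0.05 for every test, 0.05 is not the error rate of the Phase 3 comparison as a whole. The plan does not say which result would count as support for the CDST hypothesis in 4.1, or what follows if the logistic and Poisson results disagree. That choice could be made after the results are seen. A single nominal finding from a trial of 30 per group could then be carried into a larger study as evidence that the tool works.

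The same gap exists in Phase 2, which serves the primary objective: five hypothesised predictors, an open list of further ones, the same outcomes and the same two models.

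**Working it through.** **The plan's own figures.** The plan gives no family-wise error rate, so there is none to reproduce. Its only error figure is 0.05 two-sided per test (6.4.1), which is 0.025 in the direction favouring the CDST.

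**Inputs.** Four outcomes (5.2.1), two models each (6.4.3.2), 0.05 per test. The correlation between the two models' tests, r, is not in the documents and is varied as an assumption. The outcomes are first taken as independent, and each test is assumed to hold its 5% level.

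**Limits.**

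- The models always agree (4 distinct tests): 1 − 0.95^4 = 18.5%; in the CDST's favour, 1 − 0.975^4 = 9.6%.
- The models are independent (8 tests): 1 − 0.95^8 = 33.7%; in the CDST's favour, 1 − 0.975^8 = 18.3%.

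**Between the limits.** Let q be the bivariate normal probability that neither of two tests with correlation r rejects. The four-outcome rate is 1 − q^4:

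| r | Either direction | CDST's favour |
|---|---|---|
| 0.5 | 31.6% | 17.0% |
| 0.8 | 27.8% | 14.7% |
| 0.9 | 25.3% | 13.3% |
| 0.95 | 23.4% | 12.3% |

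**Plausible values of r.** A null simulation used 30 per group, 90 days, 37% adherence (the stress management proportion in 6.4.2) and a random person effect. Simple person-level tests stood in for the fitted models. The Group test and an overdispersion-corrected Poisson test correlated 0.96–0.98, giving 21–23% over four independent outcomes. Group X Time and Poisson were almost uncorrelated, giving 32–34%.

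**What moves the range.**

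- Correlated outcomes lower it. With 0.3 between outcomes, the rate is 26.1% at r = 0.8 and 21.9% at r = 0.95. If the models also agree fully, it falls below 18.5%.
- Counting Group, Group X Time and Poisson together raises it: 35–39% in the simulation, and 1 − 0.95^12 = 46.0% if all 12 tests were independent.
- Testing stress, sleep and eating separately makes six outcomes: 1 − 0.95^6 = 26.5% with one test each.

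**Phase 2.** Five predictors by four outcomes with one model is 20 tests. If all were independent, 1 − 0.95^20 = 64.2% in either direction, or 1 − 0.975^20 = 39.7% in the hypothesised direction. Independence is doubtful, since education and income are likely to be correlated.

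**The case against.** The strongest reply is that this is a pilot. Sections 4.1 and 4.3 make the CDST comparison secondary, and the stated aim is initial effect sizes, so formal multiplicity control is partly a matter of preference. That stands as a limit on the consequence. It does not remove the gap: 4.1 states a directional hypothesis, 6.4.1 sets a significance level, and 6.4.2 claims 80% power for an odds ratio of 1.28 without naming the strategy. Nor does it reach Phase 2, which is the primary objective.

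The text also hints at a lead model. The group and predictor power statements in 6.4.2 are odds ratios, and 6.4.3.1 introduces the Poisson analysis as an addition. These hints support the fix below, but they are not a rule.

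The count of eight tests is not the plan's own. Avoid overuse has no daily yes or no, preventive medication covers only some participants, and 6.4.1 could be read as offering one outcome form or the other. On a one-model reading, four tests still give 18.5% before Group X Time is counted.

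Three stronger readings are tempting, and the documents support none of them:

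- A reader might infer a 25–34% chance of a false claim for the CDST. Figures of that size count differences in either direction, and the 25% floor needs a correlation of about 0.9 that the plan does not give.
- A reader might infer that any one significant test would be declared support. The plan does not say so, and 4.1 refers to both preventive and acute strategies. The fault is that no rule is stated.
- A reader might quote 64% for Phase 2. That holds only for 20 independent two-sided tests and ignores the directions stated in 4.1.

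**Conclusion.** The point holds in a bounded form. The plan has four unranked primary outcomes, two models, 0.05 throughout and nothing decisive. For Phase 3 under no effect, the chance of at least one nominally significant group difference is about 19–34%, of which about 10–18% is the chance of one in the CDST's favour. This assumes four independent outcomes, tests that hold their level, and agreement between the two models anywhere from complete to none.

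The level assumption may fail for Poisson. The plan mentions no overdispersion correction, and in null simulations an uncorrected Poisson test rejected about 17% to 64% of the time, depending on the assumed spread between people. That is a separate issue, but it is a further reason not to let a claim rest on the Poisson test.

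The change is worth making because it is cheap. Choosing a decisive model and contrast is the firm part. Naming a single outcome for a pilot comparison is more a matter of judgement, as is narrowing the Phase 2 predictors.

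**What to change.** - In 6.4.3.1 and 6.4.3.2, name the random effects logistic model as the decisive analysis, in line with the odds ratios in 6.4.2. Make the Poisson analysis supportive, with no separate claim.
- In 6.4.3.2, state the one group contrast that decides, Group or Group X Time. Say also whether the unadjusted or adjusted version in 6.4.4 decides; otherwise that choice stays open.
- Specify a monthly rather than daily binary version of the model for avoid overuse.
- For Phase 3, either name one primary adherence outcome, which with one contrast brings the rate back to 5%, or present all outcomes as estimates with 95% confidence intervals and no significance claims, as the aim in 3.3.1 suggests.
- For Phase 2, label predictors outside those hypothesised in 4.1 as exploratory.

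The cost is analysis-plan wording, and fewer results can be called significant. Data collection and sample size do not change.

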6.4.2 Sample Size Considerations

Based on n=30 subjects in CDST and Headache Education Control groups, and assumptions of dropout rate and correlations as described in the initial phase of the study, we will have 80% power to detect an odds ratio of 1.28 in adherence to migraine management strategies between CDST and Headache Education Control.

For Phase 1b, we would like to estimate satisfaction, usability, and attrition over the course of the month of diary use. In our previous daily diary research, approximately 60% of participants do not continue using headache diary applications after 3 days, and approximately 30% of people adhere to the daily diary for the duration of a 30-day study. Therefore, we hope to obtain information from n=60 people regarding satisfaction and usability at the end of the 30-day period.

For the main phase of the study, based on estimated proportions of 0.37 for stress management, 20% with mood disorder and 30% male, cumulative drop-out rate of 0.073, 0.172 and 0.216 at the end of 1, 2, and 3 month, respectively, from previous studies 1, and assuming correlations of no more than 0.6 among repeated daily migraine management strategies, with n=100 participants, we can detect odds ratios of 1.29 between those with and without mood disorder, 1.26 between female and male, and 1.17 corresponding to 1 SD difference in continuous predictors, with 80% power.

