5.3.2 ELIGIBILITY CRITERIA

Eligibility will be determined by a phone screen provided by a research assistant, supervised by the PI.

Inclusion/Exclusion Criteria Phase 1 (A & B):

Participants will be included if they 1) have an International Classification of Headache Disorders – 3 beta diagnosis of migraine, 2) self-report between 6 to 14 headache days per month, 3) are currently prescribed a triptan for acute migraine management, 4) are between the ages of 18 and 65, and 5) self-report at least one problem with adherence to preventive and acute migraine management strategies.

Exclusion criteria are 1) probable or confirmed medication overuse headache, 2) a plan to change, or changing preventive or acute migraine medication during study participation, and 3) are pregnant or are planning to become pregnant during study involvement (as triptans are Category C medications).

Inclusion/Exclusion Criteria Phase 2:

Participants will be included if they 1) have an International Classification of Headache Disorders – 3 beta diagnosis of migraine, 2) self-report and diary-confirmed 6 to 14 headache days per month, 3) are currently using one of the following treatments for acute migraine management: triptans, ditans, gepants, NSAIDs, or acetaminophen, 4) are stable on current preventive and acute treatment regimen for migraine, 5) are between the ages of 18 and 65, 6) reads English, 7) has capacity to consent, and 8) complete 80% of diary recordings in the first 30 days of monitoring.

Exclusion criteria are 1) probable or confirmed medication overuse headache, 2) a plan to change, or changing preventive or acute migraine medication during study participation, 3) are pregnant or are planning to become pregnant during study involvement (as triptans are Category C medications), 4) psychiatric illness or cognitive difficulties that would interfere with participation in the study, and 4) participated in Phase 1 of the Clinical Decision Support for Patient Migraine Management protocol.

Inclusion/Exclusion Criteria Phase 3:

Participants will be included if they 1) completed Phase 2 of the study, 2) completed at least 80% of diary recordings throughout Phase 2 of the study, and 3) demonstrated poor (<50%) adherence to at least one acute migraine management strategy and at least one preventive behavioral migraine management strategy during study Phase 2.

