6.4.3 Planned Analyses

6.4.3.1 Primary Analyses

Primary Objective: Describe and analyze how individual differences and conditions influence adherence to preventive and acute migraine management strategies.

Phase 2 diary data will be utilized. Random effects logistic models will be used to examine the effects of individual differences (e.g., age and gender) and circumstances (headache days/last 7 days, variations in stress) on daily adherence to migraine management strategies during the initial three-month study period. The random effects logistic model is a kind of generalized linear mixed effects model which can take account of missing data due to drop outs. This type of analysis yields robust estimates even in situations when observations are missing both at random, and not at random. The total number of non-adherence days at the end of follow-up will also be obtained, and the effect of individual characteristics and conditions on the rate of non-adherence will be examined using Poisson regression model with log of length of follow-up as offset.

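### The 80% power claimed for an odds ratio of 1.28 in Phase 3 is not met at the plan's own 0.6 correlation bound: about 9% if exchangeable, about 55% if AR(1)

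*Combined protocol and SAP*

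**What the plan says.** Section 6.4.2 states that with 30 participants in each arm "we will have 80% power to detect an odds ratio of 1.28 in adherence to migraine management strategies" between the CDST and Headache Education groups. The inputs are given only by reference: "assumptions of dropout rate and correlations as described in the initial phase of the study". The only dropout and correlation assumptions in 6.4.2 are those for the main phase. There the adherence proportion is 0.37 (stress management), cumulative dropout is 0.073, 0.172 and 0.216 at months 1, 2 and 3, and the calculation proceeds "assuming correlations of no more than 0.6 among repeated daily migraine management strategies, with n=100 participants". On that basis "we can detect odds ratios of 1.29 between those with and without mood disorder, 1.26 between female and male", and 1.17 per SD of a continuous predictor, all with 80% power.

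Section 6.4.1 sets two-sided 0.05 tests and codes adherence once per day as 0 or 1. For Phase 2, section 6.4.3.1 says "Random effects logistic models will be used to examine the effects of individual differences". For Phase 3, section 6.4.3.2 says "random effects logistic models will be used to examine the effects of Group (CDST vs. Headache Education Control), Time, and Group X Time". Section 3.3.1 (Potential Benefits) describes the aim of the intervention phase as to "test the feasibility and obtain initial effect sizes for a novel tailored intervention".

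**The concern.** Group, gender and mood disorder do not vary within a person. For such contrasts, the information each participant contributes depends heavily on how strongly that person's days are correlated and on how the correlation behaves as days move apart. A cap of 0.6 is high, and 60 people is few, so an odds ratio as small as 1.28 looked out of reach.

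The plan does not say whether 0.6 applies to every pair of days (exchangeable) or to adjacent days with decay (AR(1)). The answer differs several-fold between the two, so a reader cannot tell what effect the study can detect. Someone told that Phase 3 has 80% power for 1.28 could read a null result as evidence against a modest benefit when the data could not support that reading. Gender and psychiatric comorbidity are part of the primary hypothesis in section 4.1, so the Phase 2 figures matter too.

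**Working it through.** **Inputs from the documents.** 30 per arm (6.1.2, 6.4.2); n = 100 with 20% mood disorder and 30% male; p = 0.37; the dropout above; correlation at most 0.6 (all 6.4.2); two-sided 0.05 and one binary value per day (6.4.1); three months of diary in each phase (6.3.1, 6.4.3.1).

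**Assumptions not in the documents.** 90 days; dropout spread linearly within each month (mean about 79.5 observed days); p = 0.37 for Phase 3; the correlation structure.

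**Formula.** SE(log OR) = √[1 / (I × m × p × q)], with pq = 0.37 × 0.63 = 0.2331.

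- I is n₁n₂/(n₁+n₂): 30×30/60 = 15 for Phase 3, 20×80/100 = 16 for mood disorder, 30×70/100 = 21 for gender. Per SD it is n = 100.
- m is the effective number of independent days per person. For d observed days it is d/[1+(d−1)ρ] if exchangeable and [d−(d−2)ρ]/(1+ρ) if AR(1).
- Detectable OR = exp[(1.960 + 0.842) × SE].

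**What the stated figures require.** For 80% power, m = (2.802/ln OR)² / (I × 0.2331). This gives about 36.8 effective days per person for Phase 3, 32.5 for mood disorder, 30.0 for gender and 13.7 for 1.17 per SD. The Phase 3 figure is reproduced only at an exchangeable correlation of about 0.014 or an AR(1) correlation of about 0.37. The corresponding values are 0.017 / 0.43 for mood disorder, 0.020 / 0.46 for gender and 0.059 / 0.72 per SD. If all predictors are person-level, no single correlation yields all four figures.

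**What 0.6 gives.** For 90 days, the exchangeable m is 90/(1 + 89×0.6) = 1.654 and the AR(1) m is (90 − 88×0.6)/1.6 = 23.25. Averaged over dropout they are about 1.645 and 20.6.

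- Phase 3, exchangeable: SE = √[1/(15 × 1.645 × 0.2331)] = 0.417. Detectable OR = exp(2.802 × 0.417) = 3.22.
- Phase 3, AR(1): SE = √[1/(15 × 20.6 × 0.2331)] = 0.118. Detectable OR = 1.39.

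| Contrast | Stated OR | Exchangeable 0.6: detectable OR, power at stated OR | AR(1) 0.6: detectable OR, power at stated OR |
|---|---|---|---|
| Phase 3 group | 1.28 | 3.22, 9% | 1.39, 55% |
| Mood disorder | 1.29 | 3.10, 10% | 1.38, 61% |
| Gender | 1.26 | 2.68, 10% | 1.32, 64% |
| Per SD (person-level) | 1.17 | 1.57, 16% | 1.14, 93% |

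**Sensitivity for Phase 3.**

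- Exchangeable 0.3: detectable OR 2.31, power 13%. Exchangeable 0.1: 1.66 and 28%.
- Entry to Phase 3 requires that participants "demonstrated poor (<50%) adherence to at least one acute migraine management strategy", plus the same for a preventive behavioural strategy, so the control proportion may not be 0.37. Over 0.20 to 0.50, with each arm's proportion entered separately, power at 0.6 is 7% to 9% (exchangeable) or about 44% to 58% (AR(1)).
- Different handling of dropout moves the AR(1) figure between 52% (completers only) and 62% (no dropout).

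**Cross-checks.**

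- OR 1.28 takes 0.37 to 0.429, which needs about 1,076 independent observations per arm. Dividing by 1.645 or 20.6 gives about 650 or 52 people per arm, against 30 planned.
- Random-intercept logistic models fitted to simulated data at exchangeable 0.6 (700 simulations per case) gave 9% power if 1.28 is a population-average odds ratio and 7% if it is person-specific. Reading 0.6 on the latent scale gave 12% and 8%.
- A simulated AR(1) 0.6 binary series (6,000 runs) gave 54% for Phase 3 and 64% for gender.

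**The case against.** The strongest reply is that 0.6 is a ceiling and the plan names no structure. The 9% needs days up to 89 apart to correlate as strongly as neighbouring days. The plan's own figures suggest its authors had something else in mind, since an exchangeable reading requires correlations near 0.014 to 0.020 for the three binary contrasts, and nobody would describe those as at most 0.6. Serial correlation inside the bound comes close to the stated figures: at AR(1) 0.40 (m about 34.6) the formula gives roughly 77% for Phase 3, 82% for mood disorder and 85% for gender. Phase 3 is also a pilot with a secondary comparison, and the remedy changes only wording.

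Much of this is fair as a description. The shortfall is conditional on the structure, and under AR(1) it is moderate. It does not rescue the claim. A statement of power for correlations up to 0.6 has to be true at 0.6, and under both standard structures three of the four odds ratios fail there. The plan states neither AR(1) nor 0.40. The only model it names is random-effects logistic, and with a person-level random intercept that implies the exchangeable, less favourable case; the random intercept is itself an inference, because the plan does not specify the random effects. Extra diary days do not help under exchangeability, because m cannot exceed 1/0.6 = 1.67.

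Readings that pass 80% at 0.6 need three adherence values per day, 180 days, 60 per arm, or 1.28 read as a Group × Time slope per about 45 days. The text gives one value per day, three months, 30 per group and an odds ratio between groups.

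**Conclusion.** The concern holds. The 80% power for an odds ratio of 1.28 with 30 per arm is not delivered at the plan's own correlation bound: about 9% if exchangeable and about 55% if AR(1). The Phase 2 mood-disorder and gender figures fail in the same way. The 1.17 per SD figure is met under AR(1) 0.6 and fails only for a person-level predictor under exchangeable correlation. These results rest on 90 daily values, within-month dropout taken as linear, and 0.37 carried into Phase 3; varying the Phase 3 proportion or the handling of dropout does not restore 80%.

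The finding covers the group main effect and person-level predictors. It does not cover Group × Time or predictors that vary from day to day. The treat-early outcome is seen only on days when acute medication is taken, so it has fewer observations than assumed here.

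At 0.6 the Phase 3 95% confidence interval would run from the estimated odds ratio divided by 2.26 to multiplied by 2.26 (exchangeable), or by 1.26 (AR(1)). This has to be corrected, because it is a stated numerical property of the design and it governs how a null Phase 3 result is read.

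**What to change.** Keep the sample size and revise section 6.4.2:

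- Name one correlation structure consistent with the planned random-effects model, and say what the 0.6 refers to.
- State the reference proportion for each phase, the number of days per person, and whether the odds ratios are population-average or person-specific.
- Replace the stated power and detectable odds ratios with values recomputed on that basis over a range such as 0.1, 0.3 and 0.6.
- Say whether 1.17 per SD refers to person-level or day-varying predictors.
- Drop the claim of 80% power for 1.28. Describe Phase 3 as estimating the effect size with a confidence interval and give its expected width. For the exchangeable case the multiplying factor is 2.26 at 0.6, 1.80 at 0.3 and 1.42 at 0.1. This matches the aim already given in section 3.3.1.

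The cost is a rewrite of one section. Recruitment, conduct and analysis are unchanged; the stated figures become less favourable.
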